## **8.5 ETHICAL ASPECTS**

The Sponsor, CRO, and the Investigator must comply with all instructions, regulations, and agreements in this protocol and applicable ICH and GCP guidelines, and conduct the study according to local regulations. The Investigator may delegate responsibilities for study-related tasks where appropriate to individuals sufficiently qualified by education, training, and experience, in accordance with applicable ICH and GCP guidelines. The Investigator should maintain a list of the appropriately qualified persons to whom significant study-related duties have been delegated. The Investigator is responsible for supervising those individuals and for implementing procedures to ensure the integrity of the tasks performed and any data generated.

### **8.5.1 Declaration of helsinki/good clinical practice**

The Declaration of Helsinki is the accepted basis for clinical study ethics, and must be fully followed and respected by all engaged in research on human beings. Any exceptions must be justified and stated in the protocol. The latest version of the Declaration of Helsinki is available under [www.wma.net/en/30publications/10policies/b3/index.html.pdf](http://www.wma.net/en/30publications/10policies/b3/index.html.pdf). Additionally, it is the responsibility of all engaged in research on human beings to ensure that the study is performed in accordance with the international GCP standards and according to all local laws and regulations concerning clinical studies.

### **8.5.2 Patient information and informed consent**

It is the responsibility of the Investigator to obtain written informed consent from each patient participating in this study, after adequate explanation of aim, importance, anticipated benefits, and potential hazards and consequences of the study according to applicable local laws. Written informed consent must be obtained before any study-specific procedures are performed. It must be also explained to the patient that he/she is completely free to refuse to enter the study or to withdraw from it at any time for any reason without incurring any penalty or withholding of treatment on the part of the Investigator.

With the declaration of consent the patient agrees that data on his/her medical history are recorded within the framework of the clinical study and that they are transferred to the Sponsor in a pseudo-anonymized manner. Patients will be informed that their race and ethnicity will be collected and will be used during analysis of study results.

The patient also agrees to allow the monitor/auditor/health authorities to verify the collected patient data against the patient's original medical records for the purpose of source data verification.

The ICF – personally signed and dated by the patient and the Investigator – must be kept on file by the Investigator(s) and documented in the eCRF and the patient's medical records. The Investigator confirms to the Sponsor to obtain the written informed consent from any patient before participating in the study.

If new safety information results in significant changes in the risk/benefit assessment, the consent form should be reviewed and updated if necessary. All patients (including those already being treated) should be informed of the new information and must give their written informed consent to continue in the study.

If the family doctors are informed of their patients' participation in the clinical study, this should be mentioned in the consent form.

## **8.6 INDEPENDENT ETHICS COMMITTEE/INSTITUTIONAL REVIEW BOARD AND REGULATORY AUTHORITIES**

It is the responsibility of the Sponsor to obtain and maintain independent approval from the applicable Regulatory Authorities to conduct the study in accordance with applicable regulatory requirements. It is the responsibility of the Sponsor to ensure that a positive opinion from the ECs/IRBs to conduct the study in accordance with applicable regulatory requirements is in place.

## **8.7 RECORDS**

Data collected at Screening and during the study will be recorded in the patient's source documents and retained at the study site for all patients who sign the ICF. Patients who are enrolled in the study will have their data retained in the source documents at the site and also have their data entered into the eCRF. To maintain confidentiality, the patients will be identified only by screening and patient numbers.

The completed eCRFs will be transferred to the Sponsor (or designee). Copies of each source document will be retained by the Investigator (or designee). A compact disk containing the site eCRF data will be provided to the site at the completion of the study. All source documents, records, and reports will be retained by the clinical site in accordance with 21 CFR 312.62(c). The minimum retention time for study records will meet the strictest standard applicable to that site, as dictated by any institutional requirements or local, national, or regional laws or regulations. Prior to proceeding with destruction of records, the Investigator must notify the Sponsor in writing and receive written authorization from the Sponsor to destroy study records.

In addition, the Investigator must notify the Sponsor of any changes in the archival arrangements including but not limited to archival at an offsite facility or transfer of ownership if the Investigator leaves the site.

All primary data, or copies thereof (eg, laboratory records, eCRFs, data sheets, correspondence, photographs, and computer records), which are a result of the original observations and activities of the study and are necessary for the reconstruction and evaluation of any study report, will be retained in the clinical site archives.

## 10 APPENDICES

## Appendix A CLINICAL LABORATORY EVALUATIONS

### Clinical Chemistry Panel:

Alanine aminotransferase  
Albumin  
Alkaline phosphatase  
Aspartate aminotransferase  
Blood urea nitrogen  
Calcium  
Chloride  
Creatinine  
Glucose  
Haptoglobin  
Lactate dehydrogenase (LDH)  
Potassium  
Sodium  
Total bilirubin  
Direct bilirubin  
Indirect bilirubin  
Total protein  
Uric acid

### Pregnancy Test

(for women of childbearing potential): serum test during Screening, serum or urine test at all other time points

### Systemic Lupus Erythematosus Panel:

Antinuclear antibodies (ANA) multiplex with double stranded DNA  
Anti-La/SSB antibody (SS-B)  
Anti-ribonucleoprotein antibody (RNP)  
Anti-Smith antibody (Sm)  
Anti-Ro/SSA antibody (SS-A)  
Anti-scleroderma antibody (Scl-70)  
Anti-Chromatin antibody  
Anti-Jo-1 antibody  
Anti-Centromere B antibody  
Circulating immune complexes (CIC)

### Hematology Panel:

Hematocrit  
Hemoglobin  
Mean corpuscular hemoglobin  
Mean corpuscular hemoglobin concentration  
Mean corpuscular volume  
Platelet count  
Red blood cell (RBC) count  
RBC distribution width  
Reticulocyte count  
White blood cell (WBC) count  
WBC differential (absolute):  
Basophils  
Eosinophils  
Lymphocytes  
Monocytes  
Neutrophils

### Hepatic Panel/HIV:

Hepatitis B surface antigen  
Hepatitis C virus antibody  
Human immunodeficiency virus antibody

### Coagulation Panel:

Prothrombin time or the international ratio of PT (PT-INR)  
Activated partial thromboplastin time (aPTT)  
D-dimer  
Thrombin-antithrombin assay

### Iron Panel and Erythropoietin

Erythropoietin  
Serum iron  
Total iron binding capacity (TIBC)  
Transferrin saturation  
Ferritin

### Urinalysis:

Bilirubin  
Color and appearance  
Glucose  
Ketones  
Leukocyte esterase  
Nitrite  
Occult blood  
pH and specific gravity  
Protein  
Urobilinogen  
Microscopic exam including  
bacteria, casts, crystals, epithelial cells, RBCs, and WBCs (if protein, leukocyte esterase, nitrite, or blood is positive)

### Pharmacodynamic (PD) Assays:

Complement System Classical Pathway (Wieslab-CP)  
CH50  
Total C4  
C1q  
C1s

### Gilbert's Syndrome Test

UGT1A1 gene

### Disease-Related Biomarkers

DAT (polyspecific, anti-IgG & anti-C3d)  
LDH isoforms  
Cold agglutinin (CAg) titer  
Ig subsets (IgA, IgD, IgG, IgM)  
Vaccine titers  
CAg thermal amplitude

For information on the anti-drug antibody (ADA) and PK evaluations please refer to the Laboratory Manual.

[figure not shown]
Detailed information on the allocation of samples for central or local laboratory processing is available in the Laboratory Manual.

**Appendix B CI-CTC VERSION 4.03 (CTCAE V4.03)**

[https://evs.nci.nih.gov/ftp1/CTCAE/CTCAE\\_4.03/CTCAE\\_4.03\\_2010-06-14\\_QuickReference\\_8.5x11.pdf](https://evs.nci.nih.gov/ftp1/CTCAE/CTCAE_4.03/CTCAE_4.03_2010-06-14_QuickReference_8.5x11.pdf)

**Appendix C    FUNCTIONAL ASSESSMENT OF CHRONIC ILLNESS THERAPY  
(FACIT)-FATIGUE SCALE**

**Appendix D EQ-5D-5L**

[figure not shown]

**Health Questionnaire**

[figure not shown]
**English version for the USA**

Sample

USA (English) © 2009 EuroQol Group EQ-5D™ is a trade mark of the EuroQol Group

USA (English) © 2009 EuroQol Group EQ-5D™ is a trade mark of the EuroQol Group

[figure not shown]

[figure not shown]
3

USA (English) © 2009 EuroQol Group EQ-5D™ is a trade mark of the EuroQol Group

[figure not shown]
**Appendix E 12-ITEM SHORT FORM SURVEY (SF-12)**

[figure not shown]

SAMPLE

**Appendix G HEALTHCARE RESOURCE UTILIZATION**

Healthcare resource utilization data will be collected during the Screening/Observation Period; on Day 0; on Days 21, 49, 77, 105, 133, and 161; at EOT for Part A; every 4 weeks during Part B; and at the ET/EOS visit.

For screening, please provide the healthcare resource utilization data for the past 6 months prior to the start of the Screening/Observation period.

Has the patient had any additional non-study outpatient visits, emergency room visits, or inpatient hospitalizations related to their cold agglutinin disease during the last 4 weeks?

Yes or No

If yes, please provide the information below including the number of visits.

	Yes/No	How Many
A. Extra or unscheduled (non-study) visit to the office of the study doctor	_____	_____
B. Visit to a generalist doctor	_____	_____
C. Visit to a specialist doctor	_____	_____
D. Visit to another healthcare professional (eg, nurse, therapist)	_____	_____
E. Complementary/alternative visit (eg, homeopathic, herbalist)	_____	_____
F. Visit to an urgent care or walk-in clinic (excluding a hospital emergency room)	_____	_____
G. Visit to a hospital emergency room Reason(s) for the visit (diagnosis): _____	_____	_____
H. Use of an ambulance service	_____	_____
I. Hospitalization		

Date of hospital admission \_\_\_\_\_ and date of discharge \_\_\_\_\_

Discharge diagnosis: \_\_\_\_\_

Was the patient admitted to the intensive care unit (ICU)? Yes or No

If yes, please provide dates or duration in the ICU.

[figure not shown]
Date of ICU admission: \_\_\_\_\_ and date of ICU discharge: \_\_\_\_\_

OR

Duration of ICU stay: \_\_\_\_\_

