### 4.3.3 Exploratory efficacy endpoints (Part A)

- Mean change from baseline in QOL, as assessed by the change in the five level EuroQol – five dimensions questionnaire (EQ-5D-5L) scores at the treatment assessment endpoint
- Mean change from baseline in QOL, as assessed by the change in the 12-Item Short Form Survey (SF-12®) at the end of treatment assessment endpoint
- Proportion of patients with  $\geq 12$  g/dL Hgb at treatment assessment endpoint
- Incidence of thromboembolic events after the first 5 weeks of study drug administration
- Median time to normalization of bilirubin
- Median time to normalization of LDH
- Median time to normalization of haptoglobin
- Median time to Hgb of  $\geq 12$  g/dL
- Proportion of patients normalizing haptoglobin at treatment assessment endpoint

- Proportion of patients normalizing bilirubin at treatment assessment endpoint
- Proportion of patients with abnormal LDH at baseline who normalize LDH at treatment assessment endpoint
- Patient's Global Impression of Change (PGIC) to assess the patient's perception of changes in CAgD disease burden at EOT
- Patient's Global Impression of [Fatigue] Severity (PGIS) to assess the patient's perception of changes in fatigue at EOT
- Incidence of disabling circulatory symptoms at treatment assessment endpoint
- Total healthcare resource utilization at EOT

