### **6.1.2 Day 0 visit (first dose)**

On Day 0, patients will undergo the following procedures before administration of the study drug:

- Inclusion/exclusion criteria review for confirmation of continued eligibility
- Serum or urine pregnancy test (if applicable)

- Vaccine titers
- Body weight
- Physical examination (brief)
- Vital signs
- Hematology panel
- Coagulation panel
- Clinical chemistry panel
- Urinalysis
- Solicited symptomatic anemia assessment
- QOL assessments
  - FACIT-Fatigue ([Appendix C](#))
  - EQ-5D-5L ([Appendix D](#))
  - SF-12 ([Appendix E](#))
  - PGIS (see [Appendix H](#))
  - PGIC (see [Appendix F](#))
- ADAs against BIVV009
- PK and PD sampling
- Disease-related biomarkers
- Record healthcare resource utilization data (see [Appendix G](#)) since previous assessment
- 12-lead ECG
- Record prior and concomitant medications/procedures including transfusions
- Adverse event monitoring

At 0 hour, study drug will be infused via an indwelling IV catheter over a period of 60±5 minutes. Patients with underlying cardiopulmonary disease may receive a 2-hour infusion with Sponsor approval. Additionally, study drug infusion may be interrupted or slowed in the event of suspicion of an allergic reaction or anaphylaxis.

After completion of the infusion, patients will undergo the following procedures:

- Vital signs at 1 hour (±5 minutes) postdose
- 12-lead ECG at 1 hour (±15 minutes) postdose
- PK and PD sampling at 1 hour (±15 minutes) postdose

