### 6.1.3 Weeks 1-25 Part-A

On Days 7, 21, 35, 49, 63, 77, 91, 105, 119, 133, 147, 161, and 175, patients will undergo the following procedures before administration of the study drug:

- Serum or urine pregnancy test in WOCBP (ie, women of child bearing potential), if applicable, on Days 21, 49, 77, 105, 133, and 161
- Physical examination (brief)
- Vital signs
- Hematology panel
- Clinical chemistry panel
- Solicited symptomatic anemia assessment
- QOL assessments:
  - FACIT-Fatigue: all scheduled visits
  - PGIS: Days 35, 77, and 119 only
  - PGIC: Days 35, 77, and 119 only
  - SF-12: Days 35, 77, and 119 only
  - EQ-5D-5L: Days 49, 91, and 133 only
- 12-lead ECG (Day 91 only)
- During Part A, ADA samples will be collected at predose on Day 0, 7, 35, 77, 133, 175 on Day 182 (EOT)
- PK and PD sampling
- Disease-related biomarkers (subset at Day 91 only); refer to the Laboratory Manual for details
- Record healthcare resource utilization data since previous assessment on Days 21, 49, 77, 105, 133, and 161
- Record concomitant medications/procedures including transfusions
- Adverse event monitoring

At 0 hour, study drug will be infused via an indwelling IV catheter over a period of 60 ±5 minutes. Patients with underlying cardiopulmonary disease may receive a 2-hour infusion with Sponsor approval. Additionally, study drug infusion may be interrupted or slowed in the event of suspicion of an allergic reaction or anaphylaxis.

After completion of the infusion, patients will undergo the following procedures:

- Vital signs at 1 hour (±5 minutes) postdose
- 12-lead ECG (Day 91 only) at 1 hour (±15 minutes) postdose
- PK and PD sampling at 1 hour (±15 minutes) postdose

Vaccinations should be administered according to [Section 6.1.1.1](#), if applicable, or [Appendix I](#) for Japan.

Note: Patients who miss a dose (ie, outside the dosing window or >17 days since last dose) should return to the site for an unscheduled visit 1 week prior to the next scheduled dose in order to receive an additional loading dose. The patient should then resume subsequent dosing visits every 14 days after the loading dose.

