#### **6.1.4 End-of-treatment visit in Part A (Week 26)**

On Day 182, patients will undergo the following procedures:

- Serum or urine pregnancy test (if applicable)
- Body weight
- Physical examination (full)
- Vital signs
- SLE panel
- Hematology panel
- Coagulation panel
- Clinical chemistry panel
- Urinalysis
- Solicited symptomatic anemia assessment
- QOL assessment (FACIT-Fatigue, EQ-5D-5L, SF-12, PGIS, and PGIC)
- ADAs against BIVV009 (predose) or at ET if patient withdraws early.
- PK and PD sampling
- Disease-related biomarkers
- Record healthcare resource utilization data since previous assessment
- Record concomitant medications/procedures including transfusions
- Adverse event monitoring

After completion of all Part A EOT assessments, a cross-over loading dose will be administered to patients in a blinded manner at the Week 26 visit to initiate dosing in Part B.

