#### **6.1.5.7 Early termination/end of study/safety follow-up visit**

Upon completion of dosing in the study, or if a patient terminates the study early, the following assessments should be completed 9 weeks after administration of the last dose of study drug:

- Serum or urine pregnancy test (if applicable)

- Body weight
- Physical examination (full)
- Vital signs
- SLE panel
- Hematology panel
- Coagulation panel
- Clinical chemistry panel
- Urinalysis
- Solicited symptomatic anemia assessment
- QOL assessments (FACIT-Fatigue, EQ-5D-5L, SF-12, PGIS, and PGIC)
- ADAs against BIVV009
- PK and PD sampling
- Record healthcare resource utilization data since previous assessment
- Record concomitant medications/procedures including transfusions
- Adverse event monitoring

If a patient experiences a hematological breakthrough event during the safety follow-up period, a PK, PD, and ADA sample should be collected at the time of the event.

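### Appendix G's fixed four-week recall contradicts the protocol's visit instructions, so undated healthcare-utilization counts can be duplicated or missed

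*Protocol*

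**What the plan says.** Protocol Appendix G sets the collection times: Screening, Day 0, six Part A visits between Day 21 and Day 161, the Part A end-of-treatment visit, four-weekly forms in Part B, and ET/EOS. It gives Screening its own look-back: "please provide the healthcare resource utilization data for the past 6 months prior to the start of the Screening/Observation period". For every later form the printed question covers non-study outpatient visits, "emergency room visits, or inpatient hospitalizations related to their cold agglutinin disease during the last 4 weeks". Items A to H (office, generalist, specialist, other professional, complementary, urgent care, emergency room, ambulance) take a yes/no and a count, with no dates. Hospital admissions carry admission and discharge dates, and ICU stays carry dates or a duration.

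The visit sections give a different rule. Section 6.1.3 says "Record healthcare resource utilization data since previous assessment on Days 21, 49, 77, 105, 133, and 161". Section 6.1.4 (Day 182) and Section 6.1.5.7 (ET/EOS) say "Record healthcare resource utilization data since previous assessment". Section 6.1.2 (Day 0) gives the same rule and cites Appendix G while doing so. For the ET/EOS visit, Section 6.1.5.7 adds that "the following assessments should be completed 9 weeks after administration of the last dose of study drug".

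For Part B, Section 6.1.5.2 and Table 3 footnote q require the data every 4 weeks. Neither gives a recall period or a start week for this item. The Week 27 start in Section 6.1.5.2 belongs to the pregnancy test.

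The endpoint, "Total healthcare resource utilization at EOT", is exploratory in Part A (Section 4.3.3). Section 4.3.4 lists utilization again for Part B, and the Part B SAP (Table 2) places it under the secondary objective. Both SAPs present the number of visits by type in a listing only (Part A SAP 4.5.2 and 4.5.3; Part B SAP 4.4.1.2 and 4.4.1.3).

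**The concern.** A fixed 28-day recall and a recall back to the preceding form are the same thing only when forms are exactly 28 days apart. In this schedule some intervals are shorter and some are longer. A site that reads the printed question to the patient will ask twice about some days and never about others. A site that follows the visit sections will not. With about 55 sites and nothing on the form to show which rule was used, the two kinds of record could not be told apart later.

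What is at stake is the reliability of the listed counts, above all items A to H. Without dates, a visit reported on two overlapping forms looks like two visits, and a visit in an unasked stretch leaves no trace on the form.

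**Working it through.** The documents give no figure to reproduce; the check is day arithmetic on nominal days.

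**Inputs.** Form days -42, 0, 21, 49, 77, 105, 133, 161 and 182 (Appendix G, Table 3). ET/EOS at 9 × 7 = 63 days after the last dose (Section 6.1.5.7). Printed recall 28 days after Screening (Appendix G). The Screening recall ends at the start of Screening, Day -42.

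**Formulas.** For an interval of g days between consecutive forms, overlap = max(0, 28 − g) and gap = max(0, g − 28).

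| From | To | g | Overlap | Gap |
|---|---|---|---|---|
| Day -42 | Day 0 | 42 | 0 | 14 (Days -42 to -28) |
| Day 0 | Day 21 | 21 | 7 (Days -7 to 0) | 0 |
| Day 21 | Day 161, five forms | 28 each | 0 | 0 |
| Day 161 | Day 182 | 21 | 7 (Days 154 to 161) | 0 |
| Last form before stopping | ET/EOS | 63 to 77 | 0 | 35 to 49 |

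The last row takes the final scheduled form to fall at the last dose or up to 14 days before it: 63 + 0 = 63 and 63 + 14 = 77; 63 − 28 = 35 and 77 − 28 = 49. A form completed after the last dose, for example at withdrawal, would shorten this gap.

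**Part A after first dose.** Seven forms (Days 21 to 182) × 28 = 196 days of look-back, against 182 days of follow-up. The excess of 14 days is 7 pre-dose days on the Day 21 form plus 7 repeated days on the Day 182 form. The pre-dose days were already covered by the Day 0 form. No day from Day 0 to Day 182 goes unasked.

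**First Part B form.** The start week is not stated, so only a range can be shown:

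- Week 27 (Day 189): g = 7, overlap 21
- Week 29 (Day 203): g = 21, overlap 7
- Week 31 (Day 217): g = 35, gap 7

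**With recall back to the preceding form.** Each look-back equals its interval, so overlap and gap are both 0. Part A gives 21 + 5 × 28 + 21 = 182 days for 182 days.

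Visit windows (±2 days on treatment, ±3 at Screening) move each figure by a few days.

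**The case against.** The strongest reply is that the protocol body already has the right rule. Sites that follow Sections 6.1.2, 6.1.3, 6.1.4 and 6.1.5.7 have no overlap and no gap at those visits, so the documents show a contradiction and not an error that must occur. This stands, and it is why every day count above is conditional on the printed form being followed. It does not remove the problem, because the form is what the site fills in and it asks a different question.

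A second reply is that the effect is small and lies mostly outside randomized treatment. That is largely right. Within Day 0 to 182 nothing is unasked, and the schedule is the same in both arms. The unasked stretches are in Screening and before ET/EOS. The latter is not wholly outside analysis time, though: the Part A SAP (4.1) ends the treatment period of early discontinuers at the ET/Safety Follow-up visit, and the Part B SAP (4.1) ends its period at ET/EOS.

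A third reply is that the heaviest use is captured elsewhere. Admissions are dated on the form, and adverse events requiring inpatient admission are reported as SAEs from consent to 9 weeks after the last dose (Sections 6.7 and 6.7.1.2). This stands for hospital stays. It does not help items A to H.

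A fourth reply is that the trial is well advanced. The Part A SAP gives the first randomization as 16 April 2018, and this protocol version is dated 4 November 2020, so a rewording would leave two recall rules in one dataset. The live eCRF and its completion guidelines are not available, so it is not known whether they carry the Appendix G sentence. Both points stand and shape the fix.

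**Conclusion.** This is a minor inconsistency that should be corrected. Appendix G and four procedure sections give different recall rules, and the printed rule does not fit the forms that fall off the 28-day cycle. Followed literally, it leaves 14 Screening days and at least 35 days before ET/EOS unasked, brings 7 pre-dose days onto the Day 21 form, and asks twice about 7 days late in Part A. Undated counts can then be duplicated or missed. Overlaps in them cannot be removed afterwards, whereas dated hospital stays can be de-duplicated. The figures assume nominal visit days and a last form no later than the last dose.

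Three stronger readings are tempting, and the documents support none of them:

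- A reader might infer that the total-utilization endpoint is wrong. It is only listed by visit type, with no planned sum or between-arm comparison, and it holds wherever sites followed the procedure sections. No primary or secondary conclusion depends on it. In Part B, where the SAP puts it under the secondary objective, no hypothesis is tested.
- A reader might infer event-rate bias from the share of each interval that is missed or repeated. No utilization rate or person-time denominator is specified, and the printed form may not have been followed.
- A reader might infer that the first Part B form overstates use four-fold (28 days asked over a 7-day interval) and carries placebo-period use into BIVV009 time. That needs a Week 27 start, which the protocol states only for pregnancy tests. Any overlap at that form is unknown.

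**What to change.** - Reword the Appendix G question so that it asks about use since the last healthcare-utilization assessment, with that assessment's date entered on the form. Keep the six-month recall at Screening.
- State the start week and the recall period for the four-weekly Part B forms in Section 6.1.5.2, Table 3 footnote q and Appendix G.
- For forms already collected, show in the listing the interval since the previous form and the recall wording in use, so that records under different rules can be told apart.

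The cost is one line of form wording, a short clarification for Part B and two extra listing columns. No visits, samples or analyses are added. Forms completed under the four-week wording cannot be repaired for items A to H; the extra columns only show where overlaps and gaps may lie.
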